The age range of the first cohort was chosen to enroll infants in their first influenza season with no history of prior exposure to influenza virus. Thus, this age cohort will allow examination of the true primary response to influenza infection or inactivated vaccination. Children between 6 and 12 months of age who have not previously had an influenza infection or vaccination will be eligible to participate in vaccination cohort 1A. During Visit 1, they will have an initial prevaccination blood draw and will then receive a dose of inactivated influenza vaccine. These children will then receive a booster dose of the inactivated influenza vaccine, with vaccine doses separated by 28 (+ 14) days as recommended by the AAP. A post vaccination blood draw will only be performed following the second vaccine dose [1]. To minimize blood draws, we will perform the next blood draw to interrogate the immune response following the second vaccine dose. Children between 3 and 12 months of age who present with an influenza-like illness will be eligible to participate in the infection cohort (1B). Study personnel will obtain nasal swabs from potential subjects for a rapid influenza antigen test on illness presentation (typically this occurs at day 2-4 post illness onset) if influenza testing was not completed by the clinical microbiology lab. In the event that influenza testing result is pending or completed by a medical provider, results of this test will be obtained through review of the medical record. If positive, subjects will be eligible for further study participation. Given the low sensitivity of rapid influenza testing, influenza real-time RT-PCR will be used to confirm all rapid antigen test results, with subjects recruited for further study participation if RT-PCR testing is positive. In addition, if the subject is eligible for enrollment based on a positive influenza test result by the clinical microbiology laboratory and symptomatic at the time of presentation, a nasal swab for additional influenza real time RT-PCR testing may be obtained during the first study visit (study visit 1, or visit 2 if visit 1 is bypassed) in order to obtain further information regarding the infecting influenza serotype if possible.

The age ranges of the subsequent cohorts were chosen to capture the likely exposure histories of enrolled children, specifically surrounding exposure to the 2009 pandemic H1N1 virus. All of

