5.1 Inclusion Criteria

- Age
 - Between 6 and 12 months at the time of enrollment to participate in the vaccination arm of age cohort 1A
 - Between 3 and 12 months at the time of enrollment to participate in the natural infection arm of age cohort 1B
 - > 12 months, birth date after 2009 for either the vaccination (A) or natural infection (B) arm of age cohort 2
 - Birth date between 2006 and 2009 for either the vaccination (A) or natural infection (B) arm of age cohort 3
 - Birth date between 2003 and 2006 for the vaccination (A) or natural infection (B) arm of age cohort 4
- Gestational age of ≥ 37 weeks at birth
- Parent/LAR can provide informed consent, with children ≥ 8 years of age providing informed assent
- Available for the duration of the study
- History of previous primary IIV vaccination (at least 2 previous doses for age <9 yrs, at least 1 previous dose for age 9 and older) **ONLY** for participation in the vaccination (A) arm of age cohorts 2, 3, or 4

- Acute illness documented by rapid influenza test, PCR testing, or testing done by either URM Labs or RGH Clinical Microbiology Labs to be due to influenza virus **ONLY** for participation in the natural infection arms (B) of age cohorts 1-4
- Children enrolled in the Cohort A (vaccination cohort) are required to have an appropriate weight and vital signs as determined by a licensed medical provider. Children enrolled in the Cohort B (natural infection cohort) are required to have an appropriate weight and clinically stable vital signs as determined by a licensed medical provider.
 - Children will not qualify for study participation if their weight is more than 2.5 standard deviations below population norms. This will be determined through calculation of a Z score using the PediTools website (<https://www.peditools.org/>) utilizing the appropriate CDC growth calculators for age [32].

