5.2 Exclusion Criteria

- Immunosuppression as a result of an underlying illness or condition (including HIV or a primary immunodeficiency syndrome)
- Active neoplastic disease
- Use of potentially immunosuppressive medications currently or within the past year (including chemotherapeutic agents) or chronic (>2 weeks) use of oral corticosteroid therapy
- A diagnosis of asthma requiring chronic inhaled corticosteroid use
- Participation in any clinical research study evaluating an investigational drug or therapy that is inconsistent with current standard of care within two (2) months of enrollment in this study.
- Previous administration of influenza vaccine in the current influenza season **ONLY** for subjects in the vaccination arm (A) of the study (subjects presenting with acute influenza infection with vaccine failure will be eligible to enroll in the B cohorts).
- Receipt of immunoglobulin or another blood product within the year prior to study enrollment
- An acute illness within the previous 3 days or temperature >38°C on screening **EXCEPT** for participation in the natural infection (B) cohorts
- A contraindication to influenza vaccination EXCEPT infants between 3 and 5 months presenting with natural influenza infection whose only contraindication is their current age
- Anemia in the previous 6 months (children on iron supplementation with no documentation of abnormal hemoglobin and/or hematocrit for >6 months will be allowed to participate in the study)
- Recent (within 120 days) hospitalization, excluding hospitalization for delivery or subjects enrolled in the acute cohort who have been hospitalized for influenza-related reasons
- Any medical history or other condition that the study PI feels may have a more than a minimal impact on the immune response or may impact the safety of the subject.

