ELISA: Plates will be coated with HA or NP protein and then incubated with dilutions of serum. After washing and blocking nonspecific binding, plates are incubated with a horseradish peroxidase-conjugated goat anti-human IgG antibody and developed with 3,3',5,5'-tetramethylbenzidine dihydrochloride substrate with absorbance read at 450 nm. To determine antibody avidity, sera are incubated on a recombinant HA-coated plate in the presence of serial

dilutions of sodium thiocyanate. The serum avidity is defined as the concentration of sodium thiocyanate that induces 50% inhibition of antibody binding.

Surface Plasmon Resonance (SPR): SPR measures the off rate (rate at which antibodies dissociate from the antigen) of antibody-antigen binding. The off rates provide a measure of how well the antibodies bind, indicating their quality. In an ideal immune response to vaccine, the off rates should go down, indicating an improved recognition of antigen. For these studies, collaborators at the FDA will use recombinant influenza hemagglutinins that match that year's vaccine formulation, as well as HA head only and HA stalk only recombinant proteins to measure antibody off rates.

Isolation of Influenza-Specific Monoclonal Antibodies: We will send fresh blood samples to the University of Chicago at the baseline visit and days 8+2 and 24 +/- 4 days post-vaccination or infection in study years 1 and 2 and plasmablasts (day 8) and antigen-specific memory B cells (day 24) will be isolated by flow cytometry. Monoclonal antibodies will be expressed from the cloned variable genes of single cells and the antibodies and serum will be tested for binding, neutralization, and epitope specificity. In addition, BCR repertoire will be determined using the 10x genomics platform.

Systems Biology Approaches: We will be sending PBMCs to the NIAID Systems Genomics and Bioinformatics Unit to better understand immune development in childhood. Using a combination of approaches including flow cytometry, an analysis of cellular transcriptional activity in immune cell subset and single cells as analyzed by RNA-seq or microarrays, PBMC transcriptome analysis, and additional 'omics' assays for assessing immune receptor repertoires including TCR and BCR profiling, the state of the immune system both at baseline and following immune perturbations will be assessed.

Instructions for specimen preparation, handling, and storage are described in local SOPs.

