11.4 Final Analysis Plan

Data will be analyzed at the end of the study, with results available for publication at that time.

A cohort of n=20 to 60 healthy children that receive a prime-boost vaccination with IIV and n=20 children infected with influenza acutely will be recruited for each age cohort. Their T cell and antibody responses will be measured at three time points: baseline, day 8, and day 24 post-vaccination. We will apply Shapiro-Wilk's test to check the normality. If the data passes the normality test, two sample *t*-tests will be used to detect significant mean difference between the children of different ages and flu exposures at each time point. Otherwise, Wilcoxon rank-sum test will be used. For follow up visits, subjects will be followed longitudinally for one to two years with yearly revaccination with IIV. CD4 T cell responses (flow cytometry) and B cell and antibody responses will be measured at three time points: prior to IIV re-vaccination, 8 and 24 days post re-vaccination. We will apply one-way ANOVA *F*-test (or Kruskal-Wallis test, if the

normality assumption is rejected) to detect significant group differences at each time point. Because multiple response variables are used in this analysis, the p -values will be adjusted by the Benjamini-Hochberg multiple testing procedure [38] to control the false discovery rate (FDR) at the level of 0.05.

General linear models of difference or fold change in T/B cell response at following time points from baseline will be used to explore how childhood exposures affect immune responses over time, while controlling potentially confounding variables including age, sex, presence of asthma or allergies, or other acute or chronic illnesses and medications that may impact the immune response. In addition to time-specific comparisons, the following linear mixed effect model will be used to analyze data collected from all time points

$$y_{kit} = \alpha_k + \beta_{1k}G(i) + \beta_{2k}X_{kit} + \gamma_{kt} + \dot{\mathbf{0}}_{kit}. \quad (0.1)$$

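### Cohort 1 antibody comparisons between 1A and 1B mix the infant's own response with residual maternal IgG, and section 11.4 adjusts for this only in part

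*Combined protocol and SAP*

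**What the plan says.** Section 2.2 sets up cohort 1 to "enroll infants in their first influenza season with no history of prior exposure to influenza virus", so that it shows the primary response to infection or vaccination. Section 5.1 admits infants of 6–12 months to 1A and 3–12 months to 1B, and requires "Gestational age of ≥ 37 weeks at birth". Section 5 plans 20 infants in each.

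The humoral response is an exploratory outcome (section 3.2.2), measured by ELISA, microneutralization and HAI; section 8.2.2 adds an HA antibody array. The ELISA detects bound antibody with a "horseradish peroxidase-conjugated goat anti-human IgG antibody". Section 5.2 excludes "Receipt of immunoglobulin or another blood product within the year prior to study enrollment", so passive antibody given as a product is recognised as a problem. Antibody acquired across the placenta is not mentioned anywhere.

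For season 1, section 11.4 plans three analyses:
- t-tests or Wilcoxon tests for a "significant mean difference between the children of different ages and flu exposures at each time point", with T cell and antibody responses named and no adjustment;
- "General linear models of difference or fold change in T/B cell response at following time points from baseline", fitted "while controlling potentially confounding variables including age, sex, presence of asthma or allergies" and other illnesses and medications;
- a mixed model (0.1) on the measured values, with the same list of confounders.

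None of the three includes the Visit 1 titre or the days elapsed since Visit 1.

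**The concern.** If a cohort 1 infant is naive, specific IgG present at Visit 1 is not the infant's own. It declines between visits whatever the infant does, and an IgG, HAI or neutralization readout adds what is left of it to whatever the infant makes. A change score subtracts the whole Visit 1 amount although part has already gone, so it understates the infant's response. A raw visit level includes the part still present, so it overstates it.

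This would matter less if it were the same in both arms. It is not, because eligible age and time since Visit 1 both differ between 1A and 1B. At stake is the humoral side of the one age cohort designed to contrast primary infection with primary vaccination: a difference between arms could reflect age and sampling time, and the answer could depend on which planned analysis is read. The multiplicity rule, "control the false discovery rate (FDR) at the level of 0.05", limits chance findings and does nothing about bias of this kind.

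**Working it through.** **Sampling times.** Section 7.3 puts Visits 2 and 3 at about day 36 and day 52 for two-dose children: 28 + 8 = 36 and 28 + 24 = 52, so the plan's figures reproduce. With windows (dose 2 at day 28–42; draws 8–10 and 20–28 days later), 1A is sampled 36–52 and 48–70 days after Visit 1. In 1B the draws fall at 8–10 and 20–28 days from presentation. The ranges do not overlap, so elapsed days cannot be separated from arm by adding them as a covariate.

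**Model.** Let M be maternal titre at Visit 1, R the infant's own response, t the days since Visit 1 and h the half-life. The documents give no half-life; 30–50 days is assumed.
- Observed level = M × 2^(−t/h) + R, which exceeds R by M × 2^(−t/h).
- Change = R − M × (1 − 2^(−t/h)), which falls short of R by the second term.

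**Equal M in both arms** (h = 40, Visit 3 at day 52 in 1A and day 24 in 1B). The fraction left is 0.41 and 0.66.
- M = R: change understates R by 59% in 1A and 34% in 1B; the level overstates it by 41% and 66%.
- M = 0.25 R: change understates R by 15% and 8.5%.
- M = 0.05 R: 3.0% and 1.7%.

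**Youngest eligible infant in each arm** (6 months in 1A, 3 months in 1B; 30.4 days per month; h = 40). The share of the birth titre left at Visit 1 is 4.24% and 20.59%. By Visit 3 a further 2.52% and 7.01% of the birth titre is lost, leaving 1.72% and 13.58%. Take a birth titre of 640 and R = 40 in both:
- 1A: 27 at Visit 1, 11 + 40 = 51 at Visit 3, change +24.
- 1B: 132 at Visit 1, 87 + 40 = 127 at Visit 3, change −5.

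The own responses are identical, yet change favours 1A and level favours 1B. When both infants are 6 months old the change bias reverses: 1A loses 2.52% of the birth titre and 1B loses 1.44%. The direction between arms is therefore not fixed.

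**Dependence on age.** For h = 30 to 50, the share of the birth titre left is 12–28% at 3 months, 1.5–8% at 6 months, 0.2–2.3% at 9 months and under 1% at 12 months.

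**Simulation at Visit 3.** 20 v 20 infants with identical own-response distributions, ages over the eligible ranges, half-life 30/40/50, birth geometric mean titre 160/640, own response 20/40, natural-log SD 1.0 (maternal) and 0.8 (own), detection floor 5; 12 settings of 1,500 trials, tests at 5%. Ranges cover the settings and repeated runs; bias is 1A minus 1B in log2 units.
- Raw visit level: bias −0.10 to −0.72; false rejection about 6–50%.
- Log2 change with age as covariate: bias −0.28 to +0.13; about 4–15%.
- Visit level with age and log Visit 1 titre: about 4–21%, lower than the raw level test in every setting.
- Observed minus expected residual: about 4–6% with the half-life correct; about 5–7% with it wrong, once age and Visit 1 titre are included.
- Ratio of observed to expected residual, with the same covariates: about 5–19%.

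The ratio fails because it equals 1 + R/residual, and the residual is smaller in 1A. With M = 40, R = 160, h = 40 and mid-window days 59 and 24, the residuals are 14.4 and 26.4, giving 12.1-fold in 1A and 7.1-fold in 1B for the same own response.

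**The case against.** The change model already includes age, and that matters. A plain Welch test on log2 change rejects falsely in about 6–22% of the simulated trials, and a reader might take that as the plan's error rate. It is not: section 11.4 fits change only with covariates, and with age the range is about 4–15%, within 4.7–8.6% in 11 of 12 settings in one run.

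A reader might also infer that cohort 1 baseline IgG is largely maternal. The documents do not show this. In 8 of the 12 settings, about 60–97% of 1A infants have a maternal titre at or below the detection floor. In 1B, vaccine failures may enter, the baseline is drawn after illness onset, and Visit 1 may be bypassed. Nor is the bias always an understatement; that holds for change scores only.

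The change-model sentence speaks of T/B cell response, so its use for antibody is a reading. The time-point tests do name antibody, however, and they carry the larger error with no adjustment. Finally, the outcome is exploratory, and section 11.2 disclaims precision and leaves trends to later studies. That limits the consequence; it does not make the contrast between arms interpretable.

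**Conclusion.** The point stands for the season 1 humoral comparison of 1A with 1B. The documents establish the intended naive status, the IgG readout, the different ages and sampling intervals, and the absence of any provision for maternal antibody. Followed as written, the unadjusted visit-level tests are the weakest part; the age-adjusted change model is much better but not clean.

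The size is conditional. It rests on an assumed half-life of 30–50 days and assumed birth titres, and is concentrated in infants near the lower age limits. With all infants aged 6 months or more, false rejection on raw change is only about 4–10%. It is small wherever the infant's own response is large relative to maternal titre. At most 40 of 220 children (18%) are concerned. A reader should not extend it to the CD4 T cell primary outcome, which maternal IgG does not enter. The consequence is limited to exploratory interpretation of cohort 1 antibody results.

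**What to change.** In section 11.4, for cohort 1 season 1 ELISA, HAI, microneutralization and array readouts:

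1. Do not compare 1A and 1B on unadjusted visit levels or unadjusted change. Use a model with age in months and log Visit 1 titre as covariates. On the log scale the arm coefficient is then the same whether the outcome is level or change, so the two analyses can no longer disagree. Some bias remains, which is why the second step is needed.
2. Add a decay-corrected analysis: own response = observed titre − Visit 1 titre × 2^(−actual days since Visit 1 / half-life), floored at the detection limit, then log2 transformed, with the same covariates. State one half-life in advance and repeat over a range such as 30–50 days. Do not use the ratio to expected residual for the contrast between arms, because it overcorrects.
3. Report infants whose Visit 1 was bypassed separately, since they have no baseline.

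The cost is wording in the analysis plan and a small sensitivity analysis using visit dates; no extra blood or visits. The drawback is that the corrected value depends on an assumed half-life, so the range must be shown with it.

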Natural influenza infection stimulates vigorous inflammation with activation of multiple pattern recognition receptors. This leads to a robust innate immune response characterized by production of antiviral cytokines such as interferons that both limit early viral replication and instruct developing adaptive immunity [5-8]. As the infection progresses, viral replication results in abundant intracellular antigen that can be processed and presented to activate the adaptive immune response [5,6]. While neutralizing antibodies are thought of as the major correlate of protection [9-12], cellular immunity is increasingly recognized as important in protecting from severe disease [13-16], especially as T cells can recognize conserved epitopes and provide some degree of protection in years when antigenic drift leads to a poor vaccine match or a pandemic influenza strain emerges [17-21]. In contrast to the robust responses that develop following influenza infection, the immune response generated on vaccination with IIV is characterized by weak inflammatory signaling. IIV is produced by chemical inactivation of the H1N1, H3N2, and influenza B viral strains predicted to be circulating with disruption and purification of the surface glycoproteins (HA and NA) [22-24]. This process results in production of an unadjuvanted vaccine that contains variable levels of NA, small amounts of internal virion proteins including NP, and only trace amounts of innate immune activators such as viral RNA [22,25-27].

Given the profound differences in antigenic context between natural infection and vaccination, this study will investigate how these different routes of early childhood exposure to influenza affect the functional potential of the anti-influenza immune response and determine the consequences this has on subsequent influenza vaccination. This improved knowledge of how early childhood influenza vaccination shapes the establishment of anti-influenza immunologic memory will enable both optimization of current influenza vaccination strategies and development of novel vaccines able to provide highly efficacious universal protection against both seasonal and potentially pandemic influenza strains.

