2.2 Scientific Rationale

This protocol is a population-based study that will address the hypothesis that vaccination and infection differentially drive both the CD4 T cell and B cell immunity. Recent data in the literature [3,4,28], and our own preliminary data suggest that initial encounters with influenza have a long lasting effect on both CD4 T cell and B cell mediated immunity. This protocol will address how early immunity against influenza virus is primed by vaccination versus infection and whether this differentially poises subsequent immune responses on re-challenge with influenza vaccination. We will specifically test whether the more robust pro-inflammatory response initiated on first exposure to a natural influenza infection promotes imprinting of both CD4 T cell and B cell responses, influencing long term specificity and functionality. We also will examine the effects of age and exposure on the immune response that develops following influenza vaccination. To do this, we will first examine whether early exposure to a live viral infection compared to vaccination leads to a distinct phenotype and specificity in both the B cell and CD4 T cell compartments. Subsequently, we will determine whether the CD4 T cell repertoire is remodeled over time by examining CD4 T cell specificity, cytokine production, and expression of markers and transcriptional factors associated with a negative regulatory CD4 T cell phenotype in children of different ages versus adults.

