7.2 Enrollment/Baseline (Visit 1)

Once subjects meet inclusion criteria and do not meet exclusion criteria and parents or a LAR provide consent for participation in the study, the subjects will be enrolled.

Subjects enrolled in the influenza vaccination cohorts will have a medical history obtained and demographic information collected, with particular attention to inclusion and exclusion criteria. If not already obtained, subject vital signs and weight will be measured. A targeted physical exam, focusing on the CV and respiratory systems, will then be performed as indicated by medical history. Following this, a sample of peripheral venous blood will be obtained if able. Subjects will then receive their initial influenza vaccination.

Subjects recruited with potential natural influenza infection will have a complete medical history obtained with particular attention to current symptoms of illness and inclusion and exclusion criteria. Demographic information will also be collected. If not already obtained, subject vital signs and weight will be measured. A targeted physical exam, with a focus on the respiratory and CV systems, may then be either performed by study staff or obtained from a review of the medical record. Following this, if influenza testing was not completed via the clinical microbiology lab, two nasal swabs will be obtained by placing UV-sterilized soft nylon flocked swabs into alternate nostrils of the subject and gently rotating them across the mucosa. One of these swabs will be used to perform a rapid influenza test, while the other will be placed into 1 mL of viral culture transport media for RT-PCR studies. All rapid influenza test results will be confirmed by influenza-specific RT-PCR. Subjects with negative influenza testing will not participate in the study further, although contact information will be collected and parents/LARs will be informed that we will contact them regarding possible enrollment in the full study if the influenza PCR testing comes back positive. Subjects that have a positive influenza test will have the opportunity to consent to full study participation. If this consent is obtained, a nasal wash, nasal brush, and a sample of peripheral venous blood will be collected if able. In addition, if the subject is eligible for enrollment based on a positive influenza test result performed by the clinical microbiology laboratory, a nasal swab for additional influenza real time RT-PCR testing will be obtained if

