Here y_{kit} represents the k th response variable measured from the i th subject at the t th time point; α_k is the overall mean value of y_{kit} ; $G(i)$ is a binary variable which equals 0 if the i th subject is vaccinated with IIV and 1 otherwise; β_{1k} is a linear coefficient that quantifies the magnitude of the group-effect; β_{2k} are linear coefficients for potentially confounding clinical variables listed above; γ_{kt} is a random effect term that quantifies the time effects; and $\dot{\mathbf{0}}_{kit}$ represents independent measurement errors. Likelihood ratio test will be used to test $H_0 : \beta_k = 0$ against $H_1 : \beta_k \neq 0$.

In case of high-dimensional data in different scales, standardization will be applied before model fitting and variable selection. Variable selection approaches using AIC or BIC criteria will be used to select the significant predictors. Penalized-based variable selection procedures such as LASSO [39] or SCAD [40,41] may be used to overcome the drawbacks of ad-hoc methods of stepwise, best subset selection, etc. post-hoc.

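### Model (0.1) averages the group difference over visits and has no child-level term, so it cannot test whether the cohorts respond differently to season 2 re-challenge, and its standard error is wrong

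*Combined protocol and SAP*

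**What the plan says.** Section 2.1 says the study will "determine the consequences this has on subsequent influenza vaccination", and section 2.2 asks "whether this differentially poises subsequent immune responses on re-challenge with influenza vaccination". All children, whether enrolled through vaccination (A) or infection (B), receive inactivated vaccine in season 2. They are bled before it (Visit 4) and at about days 8 and 24 after their final dose (Visits 5 and 6).

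Section 11.4 plans three kinds of analysis:

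- Group tests of level at each time point. In season 2 these are at "three time points: prior to IIV re-vaccination, 8 and 24 days post re-vaccination".
- "General linear models of difference or fold change in T/B cell response at following time points from baseline", adjusted for clinical confounders.
- Model (0.1), the only one fitted to all time points together. Its group indicator depends on the child alone, and its coefficient "is a linear coefficient that quantifies the magnitude of the group-effect". The time term depends on response variable and visit only and "is a random effect term that quantifies the time effects". The errors are taken as independent.

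Section 11.4 does not say which draw is baseline for season 2. The heading of section 7.2 equates baseline with Visit 1. Section 8.2.2 (monoclonal antibody isolation) describes sampling "at the baseline visit and days 8+2 and 24 +/- 4 days post-vaccination or infection in study years 1 and 2", which implies one baseline per year, and Appendix A labels Visit 4 as day 0.

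**The concern.** Whether infection-primed and vaccine-primed children respond differently to the same later vaccine is a question about a difference in change, that is, a group-by-visit contrast. Model (0.1) has no such term. A significant group coefficient, or a significant group test at Visit 5, could come entirely from a difference that existed before the season 2 dose, with the same rise in both groups. That would be a true finding for the general hypothesis in section 11.1, but it would not show that priming route changes the response to re-challenge.

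The model also ignores that one child contributes several visits, so the standard error of the group coefficient is too small. The same omission would make the standard error of any within-child contrast added to the model too large.

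**Working it through.** The plan gives no effect size, SD or power to reproduce; section 11.2 says the variability is unknown. The section 5 counts add up: 20 + 60 + 30 + 30 = 140 in A, 4 × 20 = 80 in B, 220 in all. By age cohort, A v B is 20 v 20, 60 v 20, 30 v 20 and 30 v 20, so the 30 v 20 figures below apply to age cohorts 3 and 4 only.

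Assumed throughout: SD 1, six visits, complete data, equal within-child correlation ρ (ICC), two-sided 0.05 before FDR adjustment, normal approximation.

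**What the coefficient estimates.** Let D_t be the B minus A mean difference at visit t. With complete data the estimate is (D_1 + … + D_6)/6.

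- Difference only after re-challenge, (0, 0, 0, 0, 0.5, 0.5): 1.0/6 = 0.17.
- Constant 0.167 at every visit: also 0.17.
- Crossing, (0, 0.5, 0.5, 0, −0.5, −0.5): 0.

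The first two patterns cannot be told apart, and the third looks like no effect.

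**Error rate as printed.** Write k = 1/nA + 1/nB. The true variance is k(1 + 5ρ)/6; the model uses k/6. At ρ = 0.5 the ratio of assumed to true SE is √(1/3.5) = 0.535, so the effective critical value is 1.96 × 0.535 = 1.05 and rejection under the null is 29%, whatever the sample size. Simulation at 140 v 80 gave 22%, 29% and 35% at ρ = 0.3, 0.5 and 0.7.

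**Re-challenge contrast.** C = (D_5 + D_6)/2 − D_4, with variance 1.5(1 − ρ)k. At 30 v 20, k = 0.0833. At ρ = 0.5 the SEs with a child effect are:

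- group coefficient: √(0.583 × 0.0833) = 0.220
- single-visit test, or change from Visit 1 to Visit 5: √0.0833 = 0.289
- C: √(0.75 × 0.0833) = 0.250

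Rejection rates for d = 0.8 SD, 30 v 20, ρ = 0.5:

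| Analysis | Difference only at Visits 5, 6 | Same difference at Visits 2 to 6 (identical re-challenge response) |
|---|---|---|
| Group coefficient, with child effect | 23% | 86% |
| Group coefficient, as printed | 58% | 98% |
| Visit 4 test | 5% | 79% |
| Visit 5 test | 79% | 79% |
| Change, Visit 1 to 5 | 79% | 79% |
| Contrast C, with child effect | 89% | 5% |

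For example, C in the first column: 0.8/0.250 = 3.2, and Φ(3.2 − 1.96) = 0.89. By the same formulae C has 83% power at 20 v 20 (SE √(0.75 × 0.1) = 0.274) and 95% at 60 v 20 (SE √(0.75 × 0.0667) = 0.224). At 140 v 80 the corrected group coefficient has 70% and C over 99%.

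Range at 30 v 20 for ρ from 0.3 to 0.7, first column: group coefficient with child effect 19–30% and C 77–99% at d = 0.8; 10–15% and 39–73% at d = 0.5.

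Adding group-by-visit terms without a child effect is not enough: C would then reject 0.6% under the null and have 67% power instead of 89%.

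**Choice of baseline.** With 140 v 80 and a 0.5 SD difference carried over from season 1, simulated change from Visit 4 rejects about 5% and change from Visit 1 rejects 85–99.8% over ρ = 0.3 to 0.7. The definition decides the answer.

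**Dose number.** Section 7.3 and Appendix A schedule two season 2 doses only for B children under 9 without two earlier doses. Suppose half of B get two, the second adds 0.5 SD, and priming route has no effect. C is then shifted by 0.5 × 0.5 = 0.25, with SE √(0.75/30 + (0.75 + 0.25 × 0.25)/20) = 0.256, and rejects 16% (8–31% if 25–75% of B get two). Restricting to one-dose children leaves 30 v 10: SE √(0.75(1/30 + 1/10)) = 0.316, power 72% for 0.8 SD (83–48% over the same range).

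**The case against.** The strongest reply is that the other planned analyses cover most of the ground. Section 11.4 tests the groups at the pre-revaccination draw as well as after it. In the carry-over case that Visit 4 test has the same 79% power as the Visit 5 test, so a reader who inferred that carry-over would go unseen would be wrong. Nor is much detection lost: the Visit 5 test finds a re-challenge-only difference 79% of the time. With complete data and the same covariates, a Visit 4-based estimate can also be recovered by subtracting two Visit 1-based coefficients. All this stands.

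It still leaves no planned test or interval for the difference in change. Comparing two p-values is a poor substitute: with equal true differences at both visits, Visit 5 is significant and Visit 4 is not in 12% of cases at 30 v 20 (16% at d = 0.5, ρ = 0.5). The subtraction also fails for B children who bypass Visit 1, which sections 5 and 7.2 allow.

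It is also fair that baseline may already mean Visit 4, given section 8.2.2 and the day 0 label. The change models would then supply the contrast and one clarifying sentence would settle that part. Section 11.4's own description of the season 2 draws names a time point and favours neither reading.

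Re-challenge appears in the background and rationale, not among the objectives and outcomes in section 3, and section 11.2 leaves any trends to later studies. That limits the weight of the point but does not remove it.

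Two further inferences are tempting and not supported. One is that the plan promises an A–B durability comparison from Visit 3 to Visit 4. Section 3.2.2 compares those visits without naming groups and refers to a post-vaccination visit, which B children do not have in year 1. The group version comes only from joining it to the exploratory objective in section 3.1. The other is that adjusting for dose number isolates priming route. No A child is scheduled for two season 2 doses, so the adjusted contrast becomes A against one-dose B children and drops the infected children under 9 with little or no vaccine history, who matter most to the priming question.

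**Conclusion.** The point holds in this form. Model (0.1) cannot test a differential response to re-challenge, and its group test is invalid with repeated visits per child. Both follow from the printed terms and need no numerical assumption beyond positive within-child correlation. The change models fill the gap directly only under one of two readings of baseline, and the documents do not choose between them. The main gain from the repair is specificity: a difference carried over from season 1 would no longer be read as an effect on re-challenge. If the A–B difference is constant after first exposure, the visit-averaged coefficient, with a correct standard error, is an adequate summary.

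The documents do not support saying that the trial cannot see carry-over or cannot address re-challenge at all; what is missing is the formal test. The power figures are illustrations on an assumed effect size, ICC and complete data. Blood is drawn only where possible and Visit 1 may be bypassed in B, so actual power would be lower. This should be corrected before analysis, but in an exploratory study it does not threaten the design.

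**What to change.** In model (0.1):

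- enter visit as a fixed factor;
- add a child-level random intercept, or an unstructured within-child covariance;
- add group-by-visit terms, with group defined as enrolment cohort (A = 0, B = 1), since every child is vaccinated by season 2.

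Name the A–B difference in change from Visit 4 to Visits 5 and 6 as the re-challenge contrast, inside the existing Benjamini-Hochberg adjustment. State that season 2 change models use the pre-revaccination draw (Visit 4) as baseline. Keep the visit-averaged difference as a further contrast and, optionally, the exploratory change from Visit 3 to Visit 4.

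Report the re-challenge contrast in all children, with a sensitivity analysis restricted to those who received one season 2 dose. State that two-dose status arises by schedule only in B children under 9 without two prior doses. The restricted result, or one adjusted by dose-by-visit terms, therefore compares A with B children who were previously vaccinated or aged 9 or over, and cannot separate dose number from vaccination history. A dose covariate that is constant over visits cancels out of the contrast and adjusts nothing.

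The cost is one variance parameter with a random intercept (more if the covariance is unstructured), five group-by-visit parameters over six visits, a few more tests in the FDR family, and lower power in the restricted analysis (72% instead of 89% in the example). No new visits, blood or data are needed; Visit 4.5 already identifies the two-dose children.
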